By nature of the size of the study, the power of the trial will be limited. The proposed primary endpoint is the between-group differences of the number of episodes, per subject, of serum K \geq 5.5 mEq/L during Weeks 3 and 4. This will be assessed as follows: Six serum samples will be collected and assessed for each patient during the efficacy phase (Weeks 3 and 4). Patients would receive a score of perfect K control (6 of 6 samples in range; Score 1.0), moderate K control (5 of 6 in range; Score 0.83), inconsistent K control (4 of 6 in range; Score 0.67), erratic K control (3 of 6 in range; Score 0.50), poor K control (2 of 6 in range; Score 0.33), very poor K control (1 of 6 in range; Score 0.17), or no K control (0 of 6 in range, Score 0). These scores will then

be averaged for the patients in the active treatment group and the control group, and the results will be compared. Using this approach, a sample size of n=20 per group provides 86% power to detect a between-group difference of 2 in mean episodes of hyperkalemia per patient, assuming $\alpha=0.05$ and standard deviation 2.

Exploratory endpoints, including those derived from the cardiac monitors, will be assessed by comparison of means and standard deviations between the two groups.

[figure not shown]
Safety Variables

Safety and tolerability variables will consist of adverse events, vital signs, ECG-parameters, clinical laboratory parameters and physical examination. Adverse Events will be summarized in an incidence table and coded to MedDRA. Laboratory parameters, vital signs and ECG-parameters will be summarized; the changes in the hematology, biochemistry parameters and vital signs from baseline will also be presented. Serious Adverse Events (SAE's) will be reported on a jointly developed form with Relypsa.

Efficacy Variables

Efficacy parameters will consist of serum levels of potassium, collected prior to scheduled dialysis treatments.

2. Study Flowchart

3. Introduction and Study Rationale

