4.2 Secondary endpoints

1. To determine whether patiromer can effectively be used in place of one dose of phosphate binder per day
2. To determine the between-group differences in percent of patients with serum $K > 5.5$ mEq/L
3. To determine the efficacy and dosing of patiromer in ESRD patients.
4. To determine the between-group differences in need for additional hemodialysis treatments due to hyperkalemia
5. To determine the between-group differences in pre-specified significant arrhythmia events as detected with cardiac monitors in Week 4.
6. To determine the between-group differences in serum albumin and PTH concentrations.
7. To determine feasibility of a large-scale hemodialysis-based trial.
8. To determine the change in serum potassium concentration two weeks after study drug is discontinued
9. To determine the change in serum phosphorus concentration two weeks after study drug has been discontinued
10. To develop procedures and instruments to be employed in a large scale clinical trial.

5. Selection and withdrawal of subjects

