6.4. Consent

Patients will be provided the Informed Consent Form and this will be reviewed by the Study Personnel. Patients will be encouraged to take the form home and review with their family if possible

6.5 Baseline period, Week 0

Once a patient has signed the ICF, a 12 lead ECG will be obtained. The long term cardiac monitor will be placed at the end of HD3 prior to Week 0 and removed at the beginning of HD3 of Week 0. Weight, pulse, and blood pressure will be recorded. Medical history and demographic data will be collected. Medications will be recorded. The hemodialysis prescription for target weight and dialysate potassium and calcium will be recorded.

Before each hemodialysis session in Week 0, blood samples will be collected and sent to the clinical laboratory. The Renal Function Panel and magnesium levels will be determined with these samples before the first dialysis session of the week (HD1). Serum pregnancy test will be measured for females of child-bearing potential.

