6.12 Concomitant medications

Except for those listed in the exclusion criteria, all medications (prescription or over-the-counter) initiated prior to enrollment may be continued during the course of the study.

All medications that are continued from the start of the study or that are started during the study (other than the study medication) including prescription or over-the-counter will be documented by the study team.

6.13 Follow-up evaluations Weeks 1, 2

A member of the study team will see the patient at the start of HD1 Week 1. Weight, pulse and blood pressure will be recorded. A pre-dialysis serum potassium lab sample will be collected and sent to the clinical lab. Concomitant medications will be recorded.

With study team visit on HD2 or HD3 of Week 1, the patiromer dose will be titrated based on the pre-dialysis potassium measured at HD1. Patiromer will be increased by 8.4 g/day if $K \geq 5.5$ meq/L, decreased by 8.4 g/day if $K < 4.5$ mEq/L, and patiromer will be discontinued if $K < 4$ mEq/L.

6.14 The assessment period Weeks 3, 4 and 6

A member of the study team will see the patient at the start of HD1 Week 3 and HD1 Week 4. Weight, pulse and blood pressure will be recorded. A pre-dialysis serum potassium lab sample will be collected and sent to the clinical lab to measure potassium. Concomitant medications will be recorded.

With study team visit on HD1 of Week 3, the patiromer dose will be titrated based on the pre-dialysis potassium measured at HD1. Patiromer will be increased by 8.4 g/day if $K \geq 5.5$ meq/L, decreased by 8.4 g/day if $K < 4.5$ mEq/L, and patiromer will be discontinued if $K < 4$ mEq/L.

The long term heart monitor (LTHM; Telepatch #2) will be placed at the end of HD3 Week 3 and removed at the beginning of HD3 of Week 4.

With study team visit on HD1 of Week 6, weight, pulse and blood pressure will be recorded. A pre-dialysis blood sample will be collected and sent to the clinical lab for a renal function panel. Concomitant medications will be recorded.

6.15. Withdrawal of subjects.

A subject may discontinue participation in the study at any time without being obligated to give a reason, although they are free to do so if they wish.

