Randomization ¹			X													
Initiation of Patiromer ²				X												
Patiromer titration ³					X			X				X		X		
Physical Exam		X														
Vital Signs ⁴ (BP, HR, Height, Weight)		X			X				X			X		X		X
Renal Function Panel		X														
Serum Potassium			X	X	X				X			X	X	X	X	X
Serum Magnesium		X							X			X				X
Serum Pregnancy Test ⁵		X														
Holter Monitor Applied	X															X
Holter Monitor Removed			X													
Previous medication and concomitant medication		X	X	X	X				X			X		X	X	X
Adverse Event Questioning		X	X	X	X				X			X		X	X	X
Dialysis ⁶																
ECG	X	←								→						

1=Randomization can occur at any point after Week 0 HD1 as long as it is completed prior to Week 0, HD3.

2=If randomized to the Patiromer Arm

3=Patiromer will be increased by 8.4 g/day if K \geq 5.1 mEq/L, decreased by 8.4 g/day if K<4.0 mEq/L, and discontinued if K<3.5mEq/L

4= Blood Pressure taken after sitting for 5 minutes; Height only collected at Week 0, HD1

5=Females of child bearing potential

6= Hemodialysis should be performed 3 times per week

BIBLIOGRAPHY

6. System USRD. 2017 USRDS annual data report: Epidemiology of kidney disease in the United States. Bethesda, MD: National Institutes of Health, National Institute of Diabetes and Digestive and Kidney Diseases; 2017.

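### Phosphorus, albumin and PTH for objectives 6 and 9, and the Week 4 HD3 QTc strips, are not matched by the visible data collection (exploratory measurements only)

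*Combined protocol and SAP*

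**What the plan says.** Sessions within a week are labelled HD1 to HD3.

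- **Objectives (section 4.2).** Objective 9: "To determine the change in serum phosphorus concentration two weeks after study drug has been discontinued". Objective 6: "To determine the between-group differences in serum albumin and PTH concentrations". Neither names the visits to be used. Section 8.2 compares laboratory values between arms by ANOVA, also without a time point, and calls the secondary measurements exploratory.
- **Laboratory draws in the visit text.** Section 6.5 places the renal function panel and magnesium at Week 0 HD1. Section 6.7 starts patiromer after Week 0 HD3, and the synopsis gives a four-week course. Section 6.13 names potassium. For HD1 of Weeks 3 and 4, section 6.14 says: "A pre-dialysis serum potassium lab sample will be collected and sent to the clinical lab to measure potassium". For HD1 of Week 6 it says: "A pre-dialysis blood sample will be collected and sent to the clinical lab for a renal function panel".
- **Schedule (section 10).** The visible laboratory rows are "Renal Function Panel", potassium, "Serum Magnesium" and the pregnancy test. No row names PTH, phosphorus or albumin.
- **QTc.** Section 8.2 plans two analyses: the mean QTc over each 7-day monitor period, and QTc from 30-second strips taken in the Week 4 HD3 session. Sections 6.10 and 6.14 take the second monitor off as that session begins. Section 6.2 describes 48-hour monitors instead.

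**The concern.** A change after stopping a drug needs one value at or near the end of treatment and one value off treatment. For phosphorus, the visible plan supplies a value before treatment and a value off treatment. The difference between them mixes any effect of the drug with its reversal, so it does not measure what objective 9 asks. Albumin has the same two draws, so its only post-randomisation comparison falls after the drug has been stopped. PTH has no visible draw. The QTc strips are assigned to a session in which the monitor is no longer worn.

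The stakes are limited to exploratory results. They still matter because section 8.1 says the study is meant to develop and test procedures for a large trial, and an on-treatment sample that was not drawn cannot be recovered later.

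**Working it through.** The plan gives no figure on this point to reproduce. The check sets each measurement against its visible source and then works out the calendar.

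**1. Visible sources**

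- Renal function panel: two draws in the text (Week 0 HD1 in 6.5, Week 6 HD1 in 6.14), none in Weeks 1 to 4.
- PTH: no draw in the text and no schedule row.
- Marks per schedule row: panel 1, magnesium 4, potassium 9, pregnancy test 1. Section 6.5 already accounts for the single panel mark. This agrees with the text but does not prove it, because the table is broken and its visible header stops at Week 4. It therefore does not show the Week 6 panel that section 6.14 requires.

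The panel's contents are not stated. I assume that it includes phosphorus and albumin. If it does not, those endpoints have no visible draw at all.

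**2. Calendar**

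Set Week 0 HD3 as day 0 and let HD1 fall three days after the previous HD3, in line with the three-day interval mentioned in section 6.2. Then HD1 of week w is day 3 + 7(w − 1), and HD3 of week w is day 7w.

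- Week 4 HD1: 3 + 21 = day 24.
- Week 4 HD3: 7 × 4 = day 28.
- Week 6 HD1: 3 + 35 = day 38.

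The date of the last dose is not stated. If four weeks means 28 daily doses, the last dose is on day 27 (first dose on day 0) or day 28 (first dose on day 1).

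- Last dose to Week 6 HD1: 38 − 27 = 11 days, or 38 − 28 = 10 days. This is short of the 14 days that two weeks implies.
- Week 4 HD1 to Week 6 HD1: 38 − 24 = 14 days, of which 3 to 4 are on drug (27 − 24 or 28 − 24) and 10 to 11 are off drug.

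A panel at Week 4 HD1 would thus be a near-end-of-treatment value, taken at the same point of the dialysis week as the Week 0 and Week 6 panels.

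**3. Monitor**

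The second monitor runs from the end of Week 3 HD3 to the start of Week 4 HD3. It covers Week 4 HD1 and HD2, which is 2 of the 3 sessions that week. In HD3 at most a strip just before removal could be obtained. The first monitor likewise covers HD1 and HD2 of Week 0. One of the two QTc analyses in section 8.2 is affected; the 7-day mean is not. On the 48-hour version in section 6.2, coverage also stops at the HD2 to HD3 interval.

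**The case against.** The strongest objection is that the laboratory gap is inferred from silence in text that is not a full laboratory list. Section 8.1 needs six samples in Weeks 3 and 4, while section 6.14 describes draws only at HD1 of each week. The visit text never mentions the on-treatment magnesium that the schedule appears to carry. The flow chart is missing, and the table does not show a Week 6 panel known to exist. An on-treatment panel could have been lost when the document was read. This stands: it lowers confidence to medium and makes confirmation by the sponsor the first step.

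Routine clinic results might also supply PTH or phosphorus, since section 6.3 already uses routine potassium values for eligibility. That is possible, but the plan names neither that source nor a date window for these endpoints.

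Objective 6 names no time point, so an albumin comparison at Week 6 is within its wording. That is true, but it would be an off-treatment comparison.

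None of this touches the QTc conflict, which lies in running text and does not depend on the table or the flow chart.

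**Conclusion.** The point holds as a mismatch between three exploratory measurements and the visible data collection. It is minor to moderate in weight, and the primary endpoint is unaffected.

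- **Phosphorus and albumin (medium confidence).** Two visible panels, none on treatment. Objective 9 lacks its end-of-treatment reference, and objective 6 can compare albumin only off treatment. This assumes that the panel contains both analytes and that no draw was lost from the table.
- **PTH (medium confidence).** No visible draw.
- **QTc strips (high confidence).** The session named in section 8.2 begins as the monitor comes off.

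A reader might infer more, and the documents do not support it:

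- *Phosphorus and albumin have no data at all.* They have Week 0 and Week 6 panels, if the panel includes them. What is missing is an on-treatment value.
- *An added panel would answer objective 1, on replacing a binder dose.* Section 6.9 says the protocol will not alter phosphate binders. No substitution is assigned, so a between-arm phosphorus comparison does not test one.
- *Recording during dialysis is lost, which is serious because section 3.1 reports 70.0% of captured arrhythmia events during dialysis in one study.* HD1 and HD2 are still recorded, and that figure concerns arrhythmias in patients with wearable defibrillators, not QTc.

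**What to change.** 1. **Confirm first.** The sponsor should check the intact schedule and flow chart for any on-treatment panel or PTH draw.
2. **Phosphorus and albumin.** If there is none, run the renal function panel on the pre-dialysis sample already drawn at Week 4 HD1, in both arms, and state that phosphorus and albumin are read from it. Use Week 4 HD1 to Week 6 HD1 for objective 9. Compare Week 4 phosphorus and albumin between arms, adjusted for the Week 0 value. State that Week 6 HD1 falls about 10 to 11 days after the last dose on the dosing assumption above.
3. **PTH.** Add it to the Week 0 and Week 4 draws, or name routine clinic values with a date window, or delete it from objective 6.
4. **QTc strips.** Take them in a Week 4 session when the monitor is worn, for example HD2, matched to Week 0 HD2. Make sections 6.2, 6.10, 6.14 and 8.2 agree on monitor duration and removal time.
5. **Objective 1.** Reconcile it with section 6.9; the added panel does not settle it.

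Cost: 40 patients × 1 = 40 extra panels on an existing draw. If PTH is added, up to 40 × 2 = 80 assays and possibly an extra tube. The rest is wording. Moving the strips changes the session named in section 8.2. Keeping HD3 by removing the monitor after the session would bring the recording to a full 7 days, which is the limit given in section 6.10 and leaves no slack.

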5.1. Informed consent

The Investigator, or a person designated by the Investigator, will fully inform the subject of all pertinent aspects of the study including the written information which has been reviewed and approved by the Institutional Review Board (IRB).

Prior to a subject's participation in the study, the Informed Consent Form will be signed and personally dated by the subject and by the person who conducted the informed consent discussion.

The Informed Consent Form used by the Investigator for obtaining the subject's informed consent will be the IRB approved version.

5.2. Inclusion criteria

1. Males and Females, age at least 18 years
2. End-stage renal disease treated with thrice-weekly hemodialysis for ≥ 3 months.
3. At least two measured pre-dialysis serum $[K] \geq 5.5$ mEq/L or one $[K] \geq 6.0$ mEq/L noted over the past three months
4. Current use of dialysate with potassium concentration = 2 mEq/L

5. Typical consumption of at least two meals per day
6. Have received customary dietary instruction over prior month
7. Considered by the treating physician(s) to be in otherwise stable clinical condition.
8. If patient is of childbearing potential, he/she will be willing to avoid pregnancy during the study using an acceptable birth control method.

5.3. Exclusion criteria

[figure not shown]
1. Not considered by the treating physician(s) to be adherent with recommended dialysis schedule and prescribed medications
2. Life expectancy < 3 months
3. Currently prescribed oral potassium supplements
4. In the prior three months, therapy with oral potassium-lowering medication
5. Underlying severe gastrointestinal disorders, including history of ischemic bowel.
6. Serum potassium concentration > 7 mEq/L in prior three months
7. Anticipated kidney transplant within the next 3 months
8. Prisoners or others who are involuntarily incarcerated or detained
9. Pregnant, breastfeeding, or considering pregnancy.
10. Participation in a clinical trial of an experimental treatment within the past 30 days

6. Trial design

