1. Not considered by the treating physician(s) to be adherent with recommended dialysis schedule and prescribed medications
2. Life expectancy < 3 months
3. Currently prescribed oral potassium supplements
4. Therapy with oral potassium-lowering medication in the prior three months,
5. Underlying severe gastrointestinal disorders, including history of ischemic bowel.
6. Corrected serum calcium concentration > 10.5 mg/dL in prior three months
7. Anticipated kidney transplant within the next 3 months
8. Prisoners or others who are involuntarily incarcerated or detained
9. Pregnant, breastfeeding, or considering pregnancy.
10. Participation in a clinical trial of an experimental treatment within the past 30 days

Duration of treatment:

Participants randomized to receive patiromer will receive the drug for a total of 4 weeks.

Withdrawal of subjects

Subjects will be withdrawn from the study and receive appropriate treatment for hyperkalemia (at the Investigator's discretion), if the serum potassium level exceeds 7 mEq/L during Week 2 to 7 and, the first sample is confirmed by a second sample exceeding 7 mEq/L at an unscheduled visit within one week.

Concomitant medications:

Subjects are not allowed to receive potassium binders during the study (e.g. sodium polystyrene sulfonate, or SPS) except in emergency situations.

Except for those listed in the exclusion criteria, all medications (prescription or over-the-counter) that have been started prior to screening may be continued during the course of the study.

Statistical analysis:

This is a proof-of-concept study, to determine the extent to which administration of patiromer has the potential to change the risk category for ESRD patients who are on conventional HD schedules. In addition, the study aims to develop and test study procedures and instruments that will be implemented in a large-scale clinical trial.

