3.2 Clinical experience with patiromer

Relypsa recognized a need for a well-tolerated potassium binder to be used in both acute and chronic clinical settings. Relypsa developed an orally administered, non-absorbed, high-capacity serum potassium binder with physicochemical characteristics that might yield an effective product suitable for chronic use. Patiromer is composed of patiromer sorbitex calcium, a new chemical entity belonging to the pharmacologic class of Potassium Binders, and xanthan gum. The product consists of the polymer anion and a calcium-sorbitol counter-ion. The polymer anion is also termed “patiromer anion” or simply “patiromer,” and it is the active moiety. The resin is a cation-exchange polymer that binds potassium predominantly in the lumen of the colon where active potassium secretion occurs. This potassium binding leads to fecal potassium excretion, leading to removal of potassium from the body and lowering of serum potassium levels in the hyperkalemic patient. On October 21, 2015 the US FDA approved patiromer for use in patients with elevated potassium concentration in the body, based on data described below in section 3.4. The approved indication in the US for patiromer is the treatment of hyperkalemia.

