6.3 Determination of eligibility

The study team will review records of prevalent Duke patients in the DaVita outpatient dialysis facilities. Patient eligibility will be determined. If routine measurements of serum potassium indicate either at least two measured pre-dialysis serum $[K] \geq 5.5$ mEq/L or one $[K] \geq 6.0$ mEq/L noted over the preceding three months, patients medical record will be reviewed to determine whether the remaining inclusion and exclusion criteria are met. The physician rounding in the dialysis unit will be asked if it is suitable to approach the patient. Eligible patients will be approached for the informed consent process.

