If a subject does withdraw from the study, the Investigator must make every effort to perform all post-study assessments. Safety and tolerability data on the subject will be evaluated and reported. The Investigator may withdraw a subject due to non-compliance with the protocol requirements, or if an event occurs which would interfere with the objectives of the study.

Subjects must be withdrawn from the study if:

1. Informed consent is withdrawn voluntarily by the subject.
2. The Investigator believes it is in the best interest of the subject to be removed from the study.
3. The serum potassium levels exceeds 7 mEq/L during Week 2 to 7 and, the first sample is confirmed by a second sample exceeding 7 mEq/L at an unscheduled visit within one week.

4. A serious adverse event occurs (the Investigator must consider severity of the event and relatedness to study medication).

5. A significant protocol violation occurs.

The date and reason for discontinuation must be noted and a brief discontinuation summary must be filled out. Serious Adverse Events should be followed up until resolution or for 30 days after discontinuation. All efforts should be made to have subjects that discontinue from study return the remainder of their study medication.

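### Exclusion criterion 6 is a serum calcium limit in the synopsis but a serum potassium limit in Section 5.3, and nothing says which list governs

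*Combined protocol and SAP*

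**What the plan says.** The exclusion criteria appear twice, in the synopsis (Section 1) and in Section 5.3, each as a complete list numbered 1 to 10.

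- Synopsis, item 6: "Corrected serum calcium concentration > 10.5 mg/dL in prior three months". This list has no upper limit on potassium.
- Section 5.3, item 6: "Serum potassium concentration > 7 mEq/L in prior three months". This list has no limit on calcium.

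Section 6.3 describes screening. Once the potassium inclusion criterion is met, the "patients medical record will be reviewed to determine whether the remaining inclusion and exclusion criteria are met". It does not say which list is meant. Section 6.12, on concomitant medication, also refers to the exclusion criteria in general ("Except for those listed in the exclusion criteria, all medications (prescription or over-the-counter) initiated prior to enrollment may be continued") and names no list.

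The 7 mEq/L threshold also appears as a withdrawal rule, in the synopsis and as item 3 of the mandatory reasons in Section 6.15: "The serum potassium levels exceeds 7 mEq/L during Week 2 to 7", with confirmation by a second sample. That rule acts after enrolment and does not settle who may enter.

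**The concern.** These are two different criteria under one number, with different analytes, thresholds and units. Neither can be read as a misprint of the other. A screener who works from the synopsis applies no potassium ceiling. One who works from Sections 5 and 6 applies no calcium limit and meets nothing there to prompt one: the only other mentions of calcium are the drug's composition (Section 3.2), intravenous calcium in emergency care (Section 3.3) and dialysate calcium (Section 6.5).

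The potassium case falls inside the target population. Inclusion 3, the same in both places, is met by one pre-dialysis value of at least 6.0 mEq/L in the past three months. A pre-dialysis value above 7 therefore helps a patient qualify under the synopsis and bars that patient under Section 5.3.

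At stake is whether entry decisions are consistent and can be audited. The documents give no reason for either criterion. Both may be protective, since Section 3.2 says of the drug that "The product consists of the polymer anion and a calcium-sorbitol counter-ion" and potassium above 7 mEq/L is the on-study withdrawal threshold, but that is inference.

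**Working it through.** **Step 1. Compare the lists item by item.**

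| Item | Subject | Synopsis and Section 5.3 |
|---|---|---|
| 1 | Adherence | Same |
| 2 | Life expectancy | Same |
| 3 | Potassium supplements | Same |
| 4 | Earlier potassium-lowering drugs | Same content, different word order |
| 5 | Gastrointestinal disorders | Same |
| 6 | Calcium (synopsis) or potassium (Section 5.3) | **Different** |
| 7 | Planned transplant | Same |
| 8 | Detention | Same |
| 9 | Pregnancy | Same |
| 10 | Other trials | Same |

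Nine of ten agree. A figure is missing near the head of Section 5.3, but the numbered list is intact, so lost text does not explain the difference. There is no amendment log that would mark either version as superseded.

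**Step 2. Look for a rule of precedence.** Sections 6.3 and 6.12 are the places where a reader would expect one. Neither names a list, and no other section does.

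**Step 3. Work out eligibility for an otherwise eligible patient** (findings in the prior three months).

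| K > 7 mEq/L | Corrected calcium > 10.5 mg/dL | Synopsis | Section 5.3 |
|---|---|---|---|
| No | No | Eligible | Eligible |
| No | Yes | Excluded | Eligible |
| Yes | No | Eligible | Excluded |
| Yes | Yes | Excluded | Excluded |

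Two of the four combinations conflict.

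**Step 4. Check the plan's own design figure.** Section 8.1 states 86% power with 20 per group, a difference of 2 episodes, SD 2 and alpha 0.05; sidedness is not stated. The noncentrality is 2 / (2 × √(2/20)) = 3.16 with 38 degrees of freedom. A two-sided t-test gives 86.9%, in line with the stated figure. No input comes from item 6. A potassium ceiling at entry could in principle change the episode rate or the SD, but the documents give no data to size that.

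**Step 5. Illustrate how often a conflict could arise.** The documents give no frequency for either finding, so this is arithmetic on an assumed share p of candidates with exactly one finding, taken as independent. Among 40 otherwise eligible candidates, the chance of at least one conflicting classification is 1 − (1 − p)^40.

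- p = 1%: 1 − 0.99^40 = 33%
- p = 1 − 0.5^(1/40) = 1.7%: 50%
- p = 10%: 1 − 0.90^40 = 99%

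This counts candidates whom the lists classify differently, not breaches. If one list alone is used, only one of the two discordant types is enrolled, so breaches would be no more frequent and usually fewer.

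**The case against.** The best case for leaving this as a minor point has four parts.

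1. The two items are compatible. Neither list requires what the other forbids, so a screener who applies both breaches neither. This stands, and it limits the defect to patients with exactly one finding. But no text tells the screener to combine the lists.
2. Section 5.3 is the dedicated eligibility section and the synopsis is only a summary, so Section 5.3 is the likely working text. That is plausible, but the documents state no such convention. Relying on it would silently drop the only serum calcium limit in the protocol.
3. Eligibility is settled before 1:1 randomization, the power is untouched, and this is a single-centre study of 40 patients with a record review and a physician check before approach. All true: no bias between arms follows, and none is claimed. The general safeguards (stable condition, the rounding physician's view) name neither threshold, and the withdrawal rule starts only in Week 2 and does not concern calcium.
4. The 33% to 99% range follows entirely from assumed frequencies. This also stands, and the range carries no weight in the conclusion.

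It is also fair to say that no withdrawal consequence is established. Section 6.15 requires withdrawal for a significant protocol violation but does not say whether an eligibility breach is one.

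**Conclusion.** The concern holds and must be fixed. One of ten exclusions contradicts its counterpart, two of four patient types receive opposite decisions, and no text resolves the conflict. This rests only on reading the two current lists side by side and needs no assumption about frequency or clinical rationale. Enrolling a patient with exactly one of the two findings breaches one list. The number of patients affected is unknown. The stated power calculation does not depend on the point, and no effect on the primary comparison is claimed. Which criterion is clinically right is not judged here.

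**What to change.** The sponsor and investigator should reconcile the synopsis and Section 5.3 so that both carry the same exclusion list, stating explicitly whether the calcium criterion, the potassium criterion or both apply. The screening form should be matched to that list. Any patient already enrolled should be checked against it and the result recorded.

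The cost is a wording change and a check of the form. Both criteria look back over the same three months, and Section 6.3 already plans a review of the medical record, so no new study visit is needed to look for either finding there. Sample size and analysis are unaffected.
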